12.7.3 Use of Antihistamines

Subjects will be advised to avoid antihistamine use 48 hours prior to each vaccine administration, the day of vaccine administration, and for 48 hours following each vaccine administration. If the subject has a pre-existing condition that requires antihistamine usage, the PI and the treating oncologist will decide if it is safe and appropriate for the subject's antihistamines to be held before and following vaccine administrations.

12.7.4 Radiologic Evaluations

Patients with progressive Grade II LGGs will be imaged by MRI as per standard of care for eligibility and baseline measurements, and to assess progression prior to vaccine therapy. Although the purpose of this study is not to detect tumor responses, any evidence of tumor response will be determined according to the Duke PRTBTC SOP (available upon request). RANO criteria⁸² will be used for overall assessment of tumor response and pseudoprogression versus progression. Progression by RANO response criteria is defined as follows: 1) New contrast-enhancing lesion outside of radiation field on decreasing, stable, or increasing doses of corticosteroids; $2 \ge 25\%$ increase in the sum of the products of perpendicular diameters between the first post radiotherapy scan, or a subsequent scan with smaller tumor size, and the scan at 12 weeks or later on stable or increasing doses of corticosteroids; 3) Clinical deterioration not attributable to concurrent medication or comorbid conditions is sufficient to declare progression on current treatment but not for entry onto a clinical trial for recurrence: 4) For patients receiving antiangiogenic therapy, significant increase in T2/FLAIR non-enhancing lesion may also be considered progressive disease. The increased T2/FLAIR must have occurred with the patient on stable or increasing doses of corticosteroids compared with baseline scan or best response after initiation of therapy and not be a result of comorbid events (e.g., effects of radiation therapy, demyelination, ischemic injury, infection, seizures, postoperative changes, or other treatment effects). Since some of these subjects will not be undergoing radiation therapy, and the possibility to exhibit pseudoprogression is likely due to inflammation from immune response at the site of the tumor, RANO criteria will be used to monitor for pseudoprogression versus progression. If pseudoprogression is suspected, the subject will continue with vaccine therapy for a minimum of 2-3 subsequent months so long as subject remains clinically and radiographically stable compared to the MRI showing suspected pseudoprogression as long as the following criteria are met: 1) the subject experiences investigator-assessed clinical benefit (i.e., no new clinical symptoms contributed to disease progression) and 2) the subject is tolerating the study treatment (i.e., no expected toxicities higher than grade 3 or unexpected toxicities). If the subject continues to do well beyond the 3 months, they will continue on study as planned.

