9.1.1 Definition of Unacceptable Toxicity

Toxicities will be graded according to the NCI CTCAE version 4 criteria. An unacceptable toxicity is defined as any Grade 3 toxicity at least possibly attributed to the vaccine (or vaccine + TMZ +/- RT) that does not resolve to baseline within 3 weeks, any Grade 3 hypersensitivity reactions requiring steroids, any Grade 4 toxicity, including neurologic events not due to progressive disease, or any life–threatening event not attributable to concomitant medication, co-morbid event, or disease progression.

Please refer to the Potential Risks Section 12.8.2 of this protocol.

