11.2 Exclusion Criteria

- 1. Prior invasive malignancy (except for non-melanomatous skin cancer) unless disease free for ≥ 3 years. (For example, carcinoma in situ of the breast, oral cavity, and cervix are all permissible.)
- 2. Metastases detected below the tentorium or beyond the cranial vault.
- 3. Severe, active co-morbidity, defined as follows:
 - a. Unstable angina and/or congestive heart failure requiring hospitalization.
 - b. Myocardial infarction within the last 6 months.
 - c. Acquired Immune Deficiency Syndrome (AIDS) based upon current CDC definition; note, however, that HIV testing is not required for entry into this protocol. The need to exclude patients with AIDS from this protocol is necessary because treatments involved in this protocol may be significantly immunosuppressive.
 - d. Major medical illnesses or psychiatric impairments that in the investigator's opinion will prevent administration or completion of protocol therapy.
- 4. Pregnant or lactating women, due to possible adverse effects on the developing fetus or infant due to study drug.
- 5. Prior allergic reaction to temozolomide.
- 6. Patients treated on any other therapeutic clinical protocols within 30 days prior to study entry or during participation in the study.
- 7. Patients with known hypersensitivity to GM-CSF, yeast-derived products, or any component of Leukine®.
- 8. Allergy or hypersensitivity to tetanus vaccine or any component of the tetanus vaccine.
- 9. Unable to undergo MRI imaging.

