12.2 Treatment Period

Patients that have consented onto this study will receive 3 vaccines as indicated above and then undergo surgical resection. Unless a patient is determined at the time of surgery to have transitioned to a higher grade brain tumor, vaccines will then continue monthly along with adjuvant cycles of TMZ on day 22 (+ 2 days) for a maximum of 15 vaccines, unless the patient has tumor progression prior to completing 12 cycles of TMZ. Subjects that have transitioned to a higher grade glioma at the time of surgery will continue on study treatment, however, they will need to undergo standard of care chemoradiation therapy. Therefore, the vaccines will be given before, during and following RT as described above. Subjects will return one month following the last vaccine for blood work (CBC and CMP) and clinical assessment to monitor for delayed toxicity.

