12.6 Early Withdrawal of Subject(s)

12.6.1 Criteria for Early Withdrawal

Subjects may voluntarily withdraw from the study at any time. The PI may also withdraw a subject from the study at any time based on his/her discretion. Reasons for PI-initiated withdrawal may include, but are not limited to the following:

• Progressive disease as documented by MRI or physical examination at any time after the initiation of post-op immunotherapy or post-RT immunotherapy (for those who've transitioned to a higher grade at time of surgery)

- Development of unacceptable toxicity, as defined in section 9.1.1
- Pregnancy
- Need for corticosteroids > 4mg/day at time of 1st vaccine
- Upon request of the subject
- If, in the investigator's medical judgment, further participation would be injurious to the subject's health or wellbeing
- Development of intolerable symptoms
- Protocol deviation
- Administrative reasons, such as a major violation of the clinical trial protocol
- Non-compliance of the subject
- Clinical decline or inability to be weaned off steroids following surgery
- Failure to undergo surgery following the 3rd vaccine
- Failure to tolerate TMZ therapy.

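### Under 12.7.4, an expected Grade 3 hypersensitivity reaction needing steroids counts as tolerating vaccine, although 9.1.1 calls it unacceptable and 12.6.1 leaves stopping to discretion

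*Combined protocol and SAP*

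**What the plan says.** Section 12.7.4 (Radiologic Evaluations) covers suspected pseudoprogression. If the subject stays clinically and radiographically stable relative to the suspicious scan, "the subject will continue with vaccine therapy for a minimum of 2-3 subsequent months", provided two criteria hold. Criterion 1 is clinical benefit as judged by the investigator. Criterion 2 is that "the subject is tolerating the study treatment (i.e., no expected toxicities higher than grade 3 or unexpected toxicities". There is no cross-reference to Section 9.1.1.

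Section 9.1.1, repeated in Sections 8 and 15.4.1, defines unacceptable toxicity without separating expected from unexpected events. It covers Grade 3 toxicity at least possibly attributed to treatment "that does not resolve to baseline within 3 weeks, any Grade 3 hypersensitivity reactions requiring steroids, any Grade 4 toxicity", and life-threatening events with no other stated cause.

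Section 12.6.1 is permissive: "The PI may also withdraw a subject from the study at any time based on his/her discretion". Among the reasons that may apply it lists "Development of unacceptable toxicity, as defined in section 9.1.1".

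Section 12.2 sets the ordinary schedule after surgery for subjects whose grade is unchanged: "vaccines will then continue monthly along with adjuvant cycles of TMZ", to a maximum of 15 vaccines, "unless the patient has tumor progression prior to completing 12 cycles of TMZ". It says nothing about toxicity.

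Section 11.2 excludes "Patients with known hypersensitivity to GM-CSF, yeast-derived products" or any Leukine component. Section 10.4.2 puts about 150 mcg of GM-CSF in each 1 mL dose.

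**The concern.** Section 12.7.4 is a stated continuation rule, and it says what tolerating treatment means. That meaning departs from the protocol's own definition of unacceptable toxicity at the point where re-dosing is most hazardous. A subject who needed steroids for a Grade 3 hypersensitivity reaction may have acquired on study the condition that would have barred entry. If the reaction is judged expected, criterion 2 still passes.

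Section 9.1 requires removal from study at definitive progression. I found no equivalent mandatory vaccine stop for toxicity in one patient: 12.6.1 permits it, 12.2 does not mention it, and the rules in 15.4.2 suspend accrual, not an individual's dosing. Section 12.7.3 advises subjects to avoid antihistamines for 48 hours either side of each vaccine, so a further dose would ordinarily be given without that cover.

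What is at stake is the safety of an occasional patient. No estimate or operating characteristic depends on it.

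**Working it through.** No figure in the plan bears on this point, so the check sets the two rules side by side and then counts doses.

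**1. The two rules compared.** 'Attributed' means at least possibly attributed to vaccine, or to vaccine with TMZ and/or RT.

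| Event | Section 9.1.1 | Criterion 2, if expected | Criterion 2, if unexpected |
|---|---|---|---|
| Grade 1–2 | not unacceptable | passes | fails |
| Grade 3, resolved within 3 weeks, not hypersensitivity needing steroids | not unacceptable | passes | fails |
| Grade 3, attributed, unresolved at 3 weeks | unacceptable | **passes** | fails |
| Grade 3 hypersensitivity needing steroids | unacceptable | **passes** | fails |
| Grade 4 or life-threatening, no other stated cause | unacceptable | fails | fails |

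Two of the four limbs of 9.1.1 pass criterion 2 when the event is expected. For unexpected events, criterion 2 is the stricter rule. Neither rule contains the other.

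**2. Is the reaction expected?** Section 12.7.4 does not define the word, so this is an assumption. In favour: 7.2.2 notes that serious allergic or anaphylactic reactions have occurred with Leukine, and 12.8.2 lists allergic reactions to both the peptide and GM-CSF, including low blood pressure and breathing difficulty. Against: 12.8.2 gives no grade and no steroid need, and it reports no toxicities in 40 patients from the group's ongoing and previous trials. Section 15.4.2 expects few or no unacceptable toxicities before surgery. It does expect some afterwards, but its figure of 18% is for TMZ alone and says nothing about hypersensitivity. Either judgement is open to the PI.

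**3. Doses.** At one vaccine a month, the 2–3 month window in 12.7.4 contains 2 to 3 vaccines. Section 12.2 already schedules those same vaccines. Added by 12.7.4: 2 − 2 = 0, or 3 − 3 = 0.

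For any subject who reacts after surgery at vaccine k, the vaccines still scheduled number 15 − k. A reaction at #4 leaves 15 − 4 = 11, and a reaction at #15 leaves 15 − 15 = 0. If the PI withdraws the subject under 12.6.1, the number is 0 at every k. This 11-to-0 range comes from 12.2 together with discretionary stopping. It is not an effect of 12.7.4.

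**4. Endpoint.** Sections 9.1.1 and 15.4.1 count the reaction whether or not vaccine continues, and so does the patient count in Table 3. Under 15.1 a patient with an unacceptable toxicity stays in the primary analysis even with fewer than 6 vaccines, so stopping early would not remove the patient either.

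**5. Should the persistent Grade 3 limb be treated the same way?** No. Table 8 in 18.5.2 answers neutrophil counts of 0.5 to below 1.0 × 10⁹/L, platelets of 10 to below 100 × 10⁹/L and Grade 3 non-hematological toxicity with TMZ delay or reduction. Section 7.3.1 reports sustained Grade 3 lymphopenia in all patients on 21-day TMZ at 100 mg/m². Subjects here start at 50 mg/m² and may rise to 100. The rate at 50 is not given, so lymphopenia alone could bring anywhere from 0% to 100% of patients under that limb. Exempting lymphopenia would not be enough, because the other toxicities in Table 8 would still be caught.

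**The case against.** The strongest reply is that 12.6.1 already deals with this. It applies at any time, names 9.1.1 toxicity, and also allows withdrawal for intolerable symptoms or when further participation would be injurious. Nothing in 12.7.4 suspends it. Section 12.7.4 sits under radiology and asks only whether a suspicious scan should end vaccine. Its criteria are preconditions for continuing, not an override. This stands as far as it goes: the PI can always stop. It does not make stopping required, and it does not correct a stated test that labels the patient as tolerating treatment.

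Second, 7.2.2 gives known GM-CSF hypersensitivity as a contraindication, so a reaction traced to GM-CSF should end dosing. That is a real safeguard. But it is background text, and it depends on attributing the reaction to one component of a mixture that also holds peptide and Montanide.

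Third, the two rules serve different ends. Section 9.1.1 defines an endpoint that deliberately takes in TMZ and RT effects, whereas criterion 2 governs one patient's continuation, so they need not match. This stands for the persistent Grade 3 limb. It does not carry over to hypersensitivity needing steroids, where continuing vaccine is the hazard itself.

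Fourth, a PI could readily call such a reaction unexpected, and criterion 2 would then fail. Also true, and it is the main reason the point is minor.

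**Conclusion.** The point holds for one kind of event. An expected Grade 3 hypersensitivity reaction needing steroids passes criterion 2 of 12.7.4, is unacceptable under 9.1.1, and leads to a vaccine stop only at the PI's discretion. It is a cheap safety improvement and not a flaw in the analysis.

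Its size is small: 0 doses beyond the 12.2 schedule, few if any of up to 28 patients (not derivable from the documents), and no change to the primary endpoint or Table 3.

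A reader might infer more than this, in three ways that the documents do not support:

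- That 12.7.4 forces re-dosing after an unacceptable toxicity. It does not, because 12.6.1 remains available throughout, and stability and criterion 1 must hold as well.
- That 12.7.4 is looser than 9.1.1 across the board. For unexpected events it is stricter.
- That criterion 2 should simply be replaced by 9.1.1. That would stop vaccine for TMZ toxicities the protocol plans to manage.

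The conclusion rests on two assumptions. One is that the reaction is judged expected. The other is that the phrase about exceeding Grade 3 applies only to expected toxicities, which is the natural reading. If it also governed unexpected ones, the gap would extend to unexpected Grade 3 reactions.

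**What to change.** Make two short edits at the next amendment:

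- In 12.6.1, add: *Vaccine stops after a Grade 3 hypersensitivity reaction requiring steroids.* This covers every subject, including those on the ordinary 12.2 schedule.
- In criterion 2 of 12.7.4, add: *and no Grade 3 hypersensitivity reaction requiring steroids*. Keep the existing bar on unexpected toxicities. On its own this edit would protect only subjects with suspected pseudoprogression.

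Neither edit needs new data, visits, patients or statistical changes. The downside is that a rare patient stops vaccine earlier, after an event the protocol already calls unacceptable.

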
12.8 Risk/Benefit Assessment

12.8.1 Potential Benefits

The potential benefits may include reduction or remission of the subject's brain cancer. Because this procedure is experimental, it cannot be guaranteed that subjects will receive any benefit as a result of participating in this research study. The information collected in this research may help scientists better understand the mechanisms involved in the immune system's ability to fight cancer. If such an understanding comes from this research, then it may benefit society by furthering the development of improved treatment methods for human malignant brain tumors in the future.

12.8.2 Potential Risks

Td

Injection of Td toxoid may produce inflammation, edema, induration, erythema, or pruritus at the injection site. Administration may cause occasional pain and discomfort up to three days after the vaccine is given.

Allergic Reactions to PEPIDH1M

Injection of antigen presenting cells may result in an allergic reaction, which could include redness and swelling at the injection site, itching, hives, low blood pressure, difficulty breathing, or in the most extreme circumstances, death. In addition, if the immune system becomes overly activated, potential discomforts may include pain, redness and swelling at the injection site.

Injection Site

EMLA ® cream, or equivalent topical analgesic, can be offered to subjects who experience local pain at the injection site.

Cerebral Edema

Cerebral edema may be secondary to the disease process itself, the surgical procedure, radiation therapy, necrosis from previous radiation, or inflammation due to immune infiltration of the brain or destruction of tumor cells. Symptoms may include, but are not limited to, severe headache, confusion,

lethargy, unresponsiveness, coma, or focal neurological deficits. Patients will be monitored throughout the course of the study and those patients with any signs or symptoms of cerebral edema may need their steroid doses increased, treatment with an osmotic diuretic, or surgical decompression. Edema that fails to respond to aggressive therapy may lead to permanent neurological impairment. The probability of this risk can be predicted to some degree based upon tumor size, location, pre-operative neurological impairment, and post-operative course prior and after PEP_{IDH1M} injections. Patients will be monitored throughout the course of the study.

Infection

The PEP_{IDH1M} vaccine injections may include the risk of infection due to potential contamination of the peptides in the laboratory. This may result in localized redness, swelling, or induration at the injection site. In the most extreme situation, this may lead to systemic bacterial/fungal sepsis and possibly death. The probability of this risk is relatively low, given the small injection volume (1 mL divided between >2 intradermal locations) and the fact that the peptides will be strictly tested for sterility prior to each injection. The risk of infection due to potential contamination of the peptides in the laboratory will be minimized by biosafety quality assurance and testing. All cell cultures will be handled under sterile conditions in a core tissue culture facility dedicated to the processing of human cells. Prior to injection into patients, peptides must pass sterility tests in thiglycolate broth, tryptic soy blood agar, and inhibitory Sabouraud agar. Following injections, patients will be monitored throughout the course of the study for any signs and symptoms of infection. There have been no infections to date in the recent VICTORI (IRB #3108-05-9R4) or ACTIVATE (IRB #5421-05-1R1) clinical trials testing similar approaches in a similar patient population. If an active infection is suspected, patients will be cultured and treated with appropriate antibiotics.

Delayed Autoimmune Diseases

It is possible that delayed autoimmune disease(s) may develop as a result of injection with PEP_{IDH1M} vaccine. This means that the immune system may be stimulated to attack natural tissue in the body. Animal studies have reported the development of autoimmunity in the context of vaccination and recovery from lymphopenia. However, our current experience with peptide vaccination in glioma patients has not demonstrated evidence of autoimmunity in treated patients. Furthermore, the doses of TMZ used in this study for induction of lymphopenia are standard doses administered to patients with gliomas. It therefore, is unknown what the risk of delayed autoimmune disease is for this study.

Phlebotomy

Drawing blood or inserting an intravenous catheter into an arm vein may result in bruising or swelling in the area of the insertion, bleeding at the site of the needle puncture, light headedness, fainting and very rarely, local infection, which may be severe. These risks are reduced by the fact that the blood will be drawn by a qualified physician, nurse or phlebotomist (a professional trained to draw blood).

Leukapheresis

As with any donation of blood, a variety of minor reactions may occur with leukapharesis, which include fainting, dizziness, or nausea. Uncommon but serious complications may also result, which include bleeding, infection, an adverse reaction to the anticoagulant or replacement fluids, hypocalcemia, hypotension, shock, convulsions, air emboli, heart failure, or the inability to transfuse blood back into the patient. These risks are reduced by the fact that the procedure will be performed by qualified staff at a specialized clinical hemapheresis unit. Patients will be carefully monitored throughout the procedure by trained nursing and medical staff. Calcium gluconate (2 gm) will be given to minimize the risks of hypocalcemia, fluid supplementation will be given to minimize hypotension.

MRI

The risks and/or discomforts associated with the performance of MRI include the anxiety produced from being in a tight, enclosed space (claustrophobia). In addition, the machine operates using a large and powerful magnet. The magnetism of the machine attracts certain metals: therefore, people with these metals in their bodies (specifically pacemakers, infusion pumps, metal aneurysm clips, metal prostheses, joints, rods or plates) will be excluded from the study if they are unable to undergo MRI imaging. Patients will also be checked to make sure that they do not bring any metal objects into the MRI facility. Dental fillings are less affected by the magnetic fields generated and are therefore permitted. It will be asked that patients let the physicians conducting this study know of any metal in their bodies other than dental fillings.

Allergic Reactions to Contrast Agents

During the MRI, patients will be given a contrast agent. The agent is given routinely to obtain enhanced MRI scans of the brain. The agent is administered through the vein and requires the placement of an IV catheter. The catheter placement is similar to drawing blood except that the catheter remains in the vein during the time the agent is actively delivered. The risks of a blood draw and insertion of a catheter are similar. There have been a few, rare cases of allergies to the agent used in MRI contrast enhanced scans. Patients with any known severe allergies to contrast agents will be excluded from the study. Patients with mild allergies (i.e., rash only) will be pretreated with Tylenol and Benadryl prior to injection of the contrast agent.

Radiation Therapy

Early side effects of radiation include hair loss, scalp redness, inflammation of the ear canals, and fatigue. In a few patients, radiation contributes to headaches or nausea. Rarely, tumors may swell during radiation causing neurological symptoms such as weakness on one side, visual loss, or changes in mental function. There is a small chance of long-term effects from radiation, occurring months or years after completion. These may include worsening of mental function, hearing, vision, strength and coordination. Rarely, radiation may cause the development of benign or malignant tumors around the brain or skull. It is unknown whether temozolomide increases the risk of any of the early or late side effects of radiation.

Temozolomide

TMZ has been well tolerated by both adults and children with the most common toxicity being mild myelosuppression. Other, less likely, potential toxicities include nausea and vomiting, constipation, headache, alopecia, rash, burning sensation of skin, esophagitis, pain, diarrhea, lethargy, hepatotoxicity, anorexia, fatigue and hyperglycemia. Hypersensitivity reactions have not yet been noted with TMZ. As in the case with many anti-cancer drugs, TMZ may be carcinogenic. Rats given TMZ have developed breast cancer. The significance of this finding for human is not presently known. TMZ therapy will be followed but given as standard of care. If toxicities occur, the Principle investigator and primary physician will titrate therapy based on standard clinical guidelines as outlined above.

GM-CSF

Injection of GM-CSF may increase the risk of infection, lower platelets, or cause fluid retention. GM-CSF also may result in an allergic reaction, which could include redness and swelling at the injection site, itching, hives, flushing, syncope, low blood pressure, difficulty breathing, or in the most extreme circumstances, death. In addition, if the immune system becomes overly activated, potential discomforts may include pain, redness and swelling at the injection site.

Montanide ISA 51

Montanide ISA 51 adjuvant is well tolerated. Local reactions may include granuloma, local pain, tenderness and erythema. Montanide ISA 51 may also cause flu like symptoms, nausea and vomiting.

Unknown Risks

The overall risk classification of this research is unknown. Clinical trials using peptide-based immunizations on brain tumor patients have only recently been published. From our experience with 40 patients in ongoing and previous trials we have not seen any toxicities or serious unexpected adverse events.

